9.2 SETTING

A retrospective cohort study will be conducted using the DoD database. The target population will include OAC treatment naïve NVAF patients with at least one prescription claim for dabigatran, rivaroxaban or apixaban (new oral anticoagulant or NOAC). For each patient treated with a NOAC, the date of the first NOAC prescription (index exposure) will serve as the index date. Only those patients whose index date occurs between the respective study periods will be included. The 12-month period prior to the index date will be defined as the pre-index period. The patients will be required to have a NVAF diagnosis in the pre-index period (including index date). Inclusion and exclusion codes can be found in [Appendix B](#).

Study period NOT including pre-index period:

- Dabigatran vs. Rivaroxaban: July 1, 2011 to June 30, 2016
- Dabigatran vs. Apixaban: December 28, 2012 to June 30, 2016

Study period including pre-index period:

- Dabigatran vs. Rivaroxaban: July 1, 2010 to June 30, 2016
- Dabigatran vs. Apixaban: December 28, 2011 to June 30, 2016

NOAC approval dates used for study period determination:

- Dabigatran (Pradaxa®) – approved October 11, 2010
- Rivaroxaban (Xarelto®) – approved July 1, 2011
- Apixaban (Eliquis®) – approved December 28, 2012

Subject Inclusion Criteria:

- Age 18+ on index date
- Patients must have been prescribed either dabigatran, rivaroxaban, or apixaban identified by pharmacy claim during the study period. The first dispensing date of either study drug will be defined as the index date;
- Patients must be treatment naïve from all OAC use prior to the first NOAC prescription, during study period.
- Patients must have at least 12 months of continuous eligibility prior to the index date;
- Patients must have at least one diagnosis code of atrial fibrillation, defined as ICD-9-CM diagnosis of 427.31 or ICD-10-CM diagnosis of I48.0, I48.1, I48.2, I48.91 on the index date or during the pre-index period.

Subject Exclusion:

- Less than 12 months of continuous eligibility in the pre-index period
- Any claim for OAC drug (oral use only) in the pre-index period
- Diagnosis of hyperthyroidism during the pre-index period

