- Having at least one claim for alternative indications; orthopedic procedures, VTE (includes DVT &PE) and the index NOAC prescription at the same time, or, the alternative indication for anticoagulant occurring within 3 months prior to index date in pre-period Having at least one claim with any of the following diagnoses or procedure codes in order to exclude patients with “transient” causes of Afib (3 months prior to index date in pre-period):
 - Cardiac surgery
 - Pericarditis
 - Myocarditis
- Having at least one medical claim with any of the following diagnoses or procedures codes in order to exclude patients with “valvular” Afib (pre-period):
 - Mitral stenosis
 - Mitral stenosis with insufficiency
 - Mitral valve stenosis and aortic valve stenosis
 - Mitral valve stenosis and aortic valve insufficiency
 - Diseases of other endocardial structures
 - Other and unspecified rheumatic heart diseases
 - Open heart valvuloplasty without replacement
 - Open and other replacement of unspecified heart valve
 - Open and other replacement of aortic valve

- Open and other replacement of mitral valve
- Open and other replacement of pulmonary valve
- Open and other replacement of tricuspid valve
- Heart valve replaced by transplant
- Heart valve replaced by a mechanical device/prosthesis
- Atrioventricular valve repair
- Aortic valve valvuloplasty
- Unlisted procedure, cardiac surgery
- Implantation of catheter-delivered prosthetic aortic heart valve; open thoracic approach
- Transthoracic cardiac exposure (e.g., sternotomy, thoracotomy, subxiphoid) for catheter-delivered aortic valve replacement; without cardiopulmonary bypass
- Transthoracic cardiac exposure (e.g., sternotomy, thoracotomy, subxiphoid) for catheter-delivered aortic valve replacement; with cardiopulmonary bypass
- Replacement, aortic valve, with cardiopulmonary bypass; with prosthetic valve other than homograft or stentless valve
- Valvuloplasty, mitral valve, with cardiopulmonary bypass
- Valvuloplasty, mitral valve, with cardiopulmonary bypass; with prosthetic ring
- Valvuloplasty, mitral valve, with cardiopulmonary bypass; radical reconstruction, with or without ring
- Replacement, mitral valve, with cardiopulmonary bypass
- Implantation of catheter-delivered prosthetic pulmonary valve, endovascular approach
- Replacement, pulmonary valve
- Valvectomy, tricuspid valve, with cardiopulmonary bypass
- Valvuloplasty, tricuspid valve; without ring insertion

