ANNEX 1. LIST OF STAND-ALONE DOCUMENTS

APPENDIX A. VARIABLE CODING LIST**Table 1. NOACs for Exposure**

Class	Description	GPI Code
Direct thrombin inhibitors	Dabigatran	833370302001
Direct Xa inhibitor	Rivaroxaban Apixaban	83370060 83370010

Table 2. Baseline Comorbid Conditions

Comorbidity		
Cancer	140.xx-172.xx, 174.xx-208.xx, 230.xx-231.xx, 233.xx-234.xx	C00.xxx-D49.xxx
Rheumatoid arthritis	714.xx	M05.xxx, M06.xxx, M08.xxx, M12.0xx
Multiple sclerosis	340	G35
Coronary artery disease	411.xx, 412.xx, 413.xx, 414.xx, 429.2	I20.x, I24.x, I25.xxx
Acute myocardial infarction	410.xx	I21.xx
Cardiomyopathy	425.xx	I42.x, I43
Ischemic stroke	433.x1, 434.x1, 436.x	I63.xxx, I67.89
TIA	435.x	G45.0, G45.1, G45.2, G45.8, G45.9, G46.0, G46.1, G46.2
Heart failure	402.x1, 404.x1, 404.x3, 428.xx	I11.0, I13.0, I13.2, I50.1, I50.2x, I50.3x, I50.4x, I50.9
Atrial flutter	427.32	I48.92
Hypertension	401.x, 402.x0, 403.xx, 404.x0, 404.x2, 405.xx	I10, I11.9, I12.x, I13.1x, I15.x, I16.x
Peripheral artery disease	440.xx, 443.xx	I70.xxx, I73.xx, I77.7x, I79.1, I79.8
Liver disease	121.1, 423.2, 570-573.xx, 751.62	B661, I311. K70.0-K77, Q446
Renal disease	580.xx-588.xx,	N0x.x, N08, B52.0, E08.2x, E09.2x, N14.x, N15.x, N17.x, N18.x, N19, N25.0, N25.1, N25.9, N25.81, N25.89, N26.x,
	590.xx-593.xx	N10, N11.x, N12, N13.0, N13.0, N13.1, N13.2, N13.30, N13.39, N13.4, N13.5, N13.6, N13.70, N13.71, N13.732, N13.729, N13.721, N13.731, N13.722, N13.739, N13.8, N13.9, N15.x, N16, N20.x, N22, N28.1, N28.0, N28.81, N28.83, N28.84, N28.85, N28.86, N28.89, N28.9, N29, R80.2
COPD/emphysema	490-492.xx, 496	J40.x-J44.x

Hypothyroidism	243-244.x	E00.x, E01.8, E02, E03.0, E03.1, E03.2, E03.3, E03.4, E03.8, E03.9, E89.0
Diabetes	250.xx	E10.xxxx, E11.xxxx, E13.xxxx
Peptic ulcer/GERD	530.11, 530.81, 536.2, 536.8, 787.1, 533.xx	K21.x, K27.x, K30, R11.10, R12
Venous thromboembolism	415.11, 415.19, 451.1x, 451.2, 451.81, 451.83, 451.84, 451.9, 453.4x, 453.8x, 453.9	I2699, I80.1x-I80.9, I82.4xx, I82.6xx, I82.890, I82.90, I82.A1x, I82.B1x, I82.C1x
Hyperlipidemia	272.0 – 272.4	E78.0x-E78.5
HIV infection	V08, 042, 079.53	Z21, B20, B97.35
Bone Marrow disease		
Thrombocytopenia	287.3, 287.4, 287.5	D69.3, D69.4x, D69.5x, D69.6
Chronic anemia	285.2	D63.x
Myelofibrosis	289.83	D75.81
Coagulopathy	286.0-286.9, 287.1, 287.3-287.5	D65-D68.x, D69.1, D69.3-D69.6
Dyspepsia	536.8	K30
Left ventricular heart failure	428.1	I50.1
Bone marrow disease	289.9	D75.9
Thrombocytopenia	287.5	D69.6
Anemia	285.9	D64.9

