	534.6x	(with hemorrhage and perforation with/without obstruction)	K28.6

	578.0	(hematemesis)	K92.0
	ICD-9 Procedure Code 44.43	(endoscopic control of gastric or duodenal bleeding)	
	CPT code 43255	(upper gastrointestinal endoscopy including esophagus, stomach, and either the duodenum and/or jejunum as appropriate with control of bleeding, any method)	
Major lower GI bleeding (Primary Only)	562.02	Diverticulosis of small intestine with hemorrhage	K55.21
	562.03	Diverticulitis of small intestine with hemorrhage	K57.11
	562.12	Diverticulosis of colon with hemorrhage	K57.13
	562.13	Diverticulitis of colon with hemorrhage	K57.31
	569.3x	Hemorrhage of rectum and anus	K57.32
	569.85	Angiodysplasia of intestine with hemorrhage	K62.5
	578.1x	Blood in stool	K92.1
	578.9	Hemorrhage of GI tract, unspecified	K92.2
Major urogenital bleed (Primary Only)	599.7	Hematuria	R31.0 - R31.29
	626.2x and (280.0, 285.1 or 285.9)	Excessive/frequent menstruation and secondary diagnosis indicating acute bleeding (anemia)	N92.0 and (D50.0, D62, D64.9)
Other major bleeds (Primary Only)	719.1x	Hemathrosis	D62
	423.0x	Hemopericardium	I31.2
	786.3x	Hemoptysis	M25.0xx
	784.7x	Epistaxis	R04.0
	459.0x	Hemorrhage not specified	R04.2
	285.1x	Acute posthemorrhagic anemia	R04.8x, R04.9, R58
TIA (Primary Only)	435.x	Transient cerebral ischemia as the principal (primary) discharge diagnosis	G45.0, G45.1, G45.8, G45.9, G46.0, G46.1, G46.2
[REDACTED]	[REDACTED]	[REDACTED]	[REDACTED]
[REDACTED]		[REDACTED]	
[REDACTED]	[REDACTED]	[REDACTED]	[REDACTED]
[REDACTED]	[REDACTED]	[REDACTED]	[REDACTED]

APPENDIX B: Inclusion and exclusion diagnosis, procedure and CPT codes**Table 1. List of codes for atrial fibrillation**

Study Inclusion DX	ICD9 Diagnosis Codes	ICD10 Diagnosis Codes
Atrial Fibrillation	427.31	I48.0, I48.1, I48.2, I48.91

Table 2. List of codes and descriptions to identify patients with exclusion diagnoses

Study Exclusion DX	ICD9 Diagnosis Codes	ICD10 Diagnosis Codes
Hyperthyroidism	242.x	E05.00, E05.01, E05.10, E05.11, E05.20, E05.21, E05.30, E05.31, E05.40, E05.41, E05.80, E05.81, E05.90, E05.91
Orthopedic Procedures (See also procedure codes)	V43.64, V43.65	Z9664x, Z9665x
DVT	451.xx, 453.xx	I80.xxx, I82.xxx
PE	415.1x	I26.01, I26.09, I26.90, I26.92, I26.99, I27.82
Pericarditis	391.x, 393, 420.x, 423.2, 036.41, 074.21, 093.81, 098.83	A39.53, B33.23, I01.0, I09.2, I30.0, I30.1, I30.8, I30.9, I31.0, I32, M32.12

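### ICD-9 423.2 is both a pericarditis exclusion code (Appendix B) and a liver-disease covariate code (Appendix A), and its ICD-10 partner I31.1 is missing from the exclusion

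*Combined protocol and SAP*

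**What the plan says.** Section 9.2 states that "Inclusion and exclusion codes can be found in" Appendix B. Among the transient causes of AF, one claim for pericarditis in the 3 months before index excludes a patient.

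- **Pericarditis exclusion (Appendix B Table 2).** The ICD-9 side reads "391.x, 393, 420.x, 423.2, 036.41, 074.21, 093.81, 098.83". The ICD-10 side has four I30 codes (.0, .1, .8, .9), I31.0, I32, I01.0, I09.2, A39.53, B33.23 and M32.12. It does not have I31.1.
- **Liver disease covariate (Appendix A Table 2).** The ICD-9 side reads "121.1, 423.2, 570-573.xx, 751.62". The ICD-10 side has four entries in this order: B661, I311 (followed by a stray full stop), the range K70.0 to K77, and Q446.
- **Use of the covariate.** Section 9.3.3 lists liver disease as a baseline comorbidity. It is captured over 12 months by one inpatient claim or two office or emergency visits. Section 9.7 considers the relevant comorbidities for the propensity score.

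On the secondary matter, Section 9.2 excludes a claim for "VTE (includes DVT &PE) and the index NOAC prescription at the same time", or such an indication "occurring within 3 months prior to index date in pre-period". The DVT row in Appendix B Table 2 gives the whole ICD-9 families 451 and 453 and, in ICD-10, "I80.xxx, I82.xxx". The PE row has 415.1x in ICD-9, and its ICD-10 side includes I27.82. The VTE covariate in Appendix A Table 2 is selective: "415.11, 415.19, 451.1x, 451.2, 451.81, 451.83, 451.84, 451.9, 453.4x, 453.8x, 453.9" in ICD-9, and in ICD-10 "I2699, I80.1x-I80.9, I82.4xx, I82.6xx, I82.890, I82.90" plus the I82.A1, I82.B1 and I82.C1 groups.

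**The concern.** One code cannot mean pericarditis when it excludes a patient and liver disease when it describes one, unless the plan gives a reason. It gives none. Two things follow. Eligibility depends on which code system a claim was written in, although the condition is the same. And a code that the plan itself treats as pericarditis can set a liver-disease flag in patients who remain, and that flag is a candidate for the propensity model. Both are errors of specification that a programmer following the appendices would carry into the analysis data set.

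**Working it through.** The plan states no figure on this point, so the check sets the code lists side by side.

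**Step 1: the pairing.** The Liver disease row has four entries on each side. Read in order they pair as 121.1 with B661, 423.2 with I311, 570-573 with K70.0-K77, and 751.62 with Q446. Two other places support this reading. Appendix A Table 7 also sets the 571-573 liver codes against the K70-K77 range. Appendix A Tables 7 and 9 contain 423.0x and I31.2, so the 423 and I31 families go together elsewhere in the plan.

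**Step 2: what happens to a patient with this condition.**

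| Code and timing | Excluded as pericarditis? | Can count as liver disease? |
|---|---|---|
| 423.2, within 3 months of index | Yes | Not relevant (excluded) |
| 423.2, earlier in the 12 months | No | Yes, if the claim threshold is met |
| I31.1, within 3 months of index | No | Yes, if the claim threshold is met |
| I31.1, earlier in the 12 months | No | Yes, if the claim threshold is met |

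Rows 1 and 3 differ only in the code system.

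**Step 3: how far the covariate error spreads.** Neither 423.2 nor I31.1 appears in the liver components of the Charlson index (Appendix A Table 4) or of HAS-BLED (Appendix A Table 7). Those scores are unaffected. The error is confined to the separate Liver disease flag.

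**Step 4: the DVT row against the VTE covariate list.** A set difference gives the codes caught by the exclusion but absent from the covariate list.

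- ICD-9: 451.0, 451.82, 451.89, 453.0 to 453.3, 453.5x, 453.6, 453.7x.
- ICD-10: I80.0x, I82.0, I82.1, I82.2xx, I82.3, I82.5xx, I82.7xx, I82.81x, I82.891, I82.91, I82.A2x, I82.B2x, I82.C2x.

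The row is broad on both sides, so the breadth itself creates no difference between code systems. I27.82 in the PE row is a separate point: it has no ICD-9 counterpart beyond 415.1x.

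**Step 5: would a broad DVT row cost power?** Section 9.5 gives 16,000 dabigatran patients, 10% matching loss, 3.1% per year and 0.82 years. With 1:1 matching, n = 16,000 × 0.9 = 14,400 per group.

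- Events = n × 0.031 × 0.82 × (1 + HR) = 14,400 × 0.02542 × 2.22 = 813 for a 22% difference.
- Power = Φ(√events / 2 × ln HR − 1.96) = Φ(28.51 / 2 × 0.1989 − 1.96) = 0.809. This reproduces the stated 80%.
- The apixaban comparison, with 5,400 per group and HR 1.37, gives 325 events and power 0.810, again the stated 80%.
- If a further 0.5% of dabigatran patients were lost (an assumption), power would be 0.807 and 0.808. At 5% it would be 0.789 and 0.790.

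**The case against.** **On 423.2.** The row may have been meant to use I31.0, which is in the pericarditis list, as the ICD-10 partner of 423.2. Then Appendices A and B would translate the same code differently, which is still a conflict to settle. It can also be said that the effect is tiny, that liver disease is only a candidate for the propensity model, and that month and year of index in that model limit any effect of a change of code system on the comparison. All of that stands. It bears on size, not on whether the lists are wrong.

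**On the DVT row.** A reader might infer that eligible AF patients are wrongly removed for superficial phlebitis, because codes such as 451.0, 451.82, 453.6, I80.0x and I82.81x fall in the exclusion but not in the covariate list. The documents do not support that as an error.

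- The lists do different jobs. One defines a covariate with a stricter claim threshold; the other is a one-claim screen for another reason to start the drug. A sensitive screen is defensible, since every patient has an AF code and that code alone does not show why the drug was given.
- The documents give no titles for these codes; calling them superficial rests on standard ICD nomenclature. On that same nomenclature the covariate list is not free of superficial veins (453.8x, I80.8 and I82.6xx can include them), so it is no clean standard. Part of the surplus (chronic, vena cava, renal and hepatic vein thrombosis) may well belong in the exclusion.
- If 0.2% to 0.5% of starters were affected, that would be 84 to 209 of 16,604 + 25,215 = 41,819 patients, and 54 to 135 of 6,050 + 20,930 = 26,980. That rate is an assumption with no source in the documents, and the denominators are feasibility counts that the abstract expects to shrink.

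What remains is that the plan does not explain the breadth and labels the row DVT.

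**Conclusion.** The point holds for 423.2 and I31.1. The plan gives 423.2 two incompatible roles, and the pericarditis exclusion lacks the ICD-10 code that the plan pairs with it. This rests on reading the Liver disease row in order and on taking I311 as I31.1; both should be checked against the code manual. The number of patients cannot be derived from the documents and should be very small. No difference between treatment groups is shown, and the Charlson and HAS-BLED scores are untouched. The breadth of the DVT row and the I27.82 entry are matters for confirmation, not demonstrated errors.

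**What to change.** 1. In Appendix B Table 2, add I31.1 to the ICD-10 Pericarditis list.
2. In Appendix A Table 2, remove 423.2 and I31.1 from Liver disease.
3. Add a sentence stating whether the DVT row is meant as a broad screen for other indications. If it is not, align the label with the codes. In the same place, confirm whether I27.82 is intended, given that the ICD-9 side has only 415.1x.

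The cost is two code-list edits and one sentence, with the cohort and the Liver disease flag derived from the corrected lists. The design and the analysis model do not change.

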9.11 BIAS

As for any observational study, there are many potential sources of bias, and there may be significant sources of bias that are not recognized. To minimize bias, this study will include only patients who have not previously been treated with novel oral anticoagulation, and will use propensity score IPTW. Further, effort has been made to avoid exclusions that may differentially affect the treatment groups, and be a potential bias.

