Myocarditis	391.2, 422.xx, 074.23, 398.0, 429.0, 032.82, 036.43, 093.82, 130.3	A36.81, A38.1, A39.52, A52.06, A54.83, B26.82, B33.22, B58.81, D86.85, I01.2, I09.0, I40.0, I40.1, I40.8, I41, I511.4, J10.82, J11.82
Pulmonary Embolism	415.1x	I26.01, I26.09, I26.90, I26.92, I26.99, I27.82
Valvular Afib		
Mitral stenosis	394.0x	I05.0, I05.1, I05.2, I05.8, I05.9, I34.2
Mitral stenosis with insufficiency	394.2	I34.0, I34.2, I34.8, I34.9
Mitral valve stenosis and aortic valve stenosis	396.0	I06.0, I35.0, Q23.0
Mitral valve stenosis and aortic valve insufficiency	396.1	I08.0, I06.1, I25.1, Q23.1, Q23.8, Q23.9

Diseases of other endocardial structures	397.x	I07.x, I09.89, I08.1, I08.2, I08.3, I08.8, I08.9
Other and unspecified rheumatic heart diseases	398.9x	I09.9, I09.81, I09.89
Heart valve replaced by transplant	V42.2	Z95.3, Z95.4
Heart valve replaced by a mechanical device/prosthesis	V43.3	Z95.2
Atrioventricular valve repair	V43.3	Z95.2
Aortic valve valvuloplasty/diseases of aortic valve	395.x	I06.x

Table 3. List of codes and descriptions to identify patients with exclusion procedures

Subject Exclusion Criteria:	ICD9 Procedure Codes	ICD10 Procedure Codes	CPT Codes
Valvular Afib Procedure/CPT codes			
Open heart valvuloplasty without replacement	35.1x	02QF0ZZ, 02QG0ZZ, 02QH0ZZ, 02QJ0ZZ, 027F04Z, 027F0DZ, 027F0ZZ, 02NF0ZZ, 02QF0ZZ, 027G04Z, 027G0DZ, 027G0ZZ, 02NG0ZZ, 02QG0ZZ, 027H04Z, 027H0DZ, 027H0ZZ, 02NH0ZZ, 02QH0ZZ, 027J04Z, 027J0DZ, 027J0ZZ, 02NJ0ZZ, 02QJ0ZZ	

Open And Other Replacement Of Heart Valve (This includes : Open and other replacement of unspecified heart valve, Open and other replacement of aortic valve, Open and other replacement of mitral valve , Open and other replacement of mitral valve , Open and other replacement of pulmonary valve, Open and other replacement of tricuspid valve.)	35.2x	02RF07Z, 02RF08Z, 02RF0JZ, 02RF0KZ, 02RF47Z, 02RF48Z, 02RF4JZ, 02RF4KZ, 02RG07Z, 02RG08Z, 02RG0JZ, 02RG0KZ, 02RG47Z, 02RG48Z, 02RG4JZ, 02RG4KZ, 02RH07Z, 02RH08Z, 02RH0JZ, 02RH0KZ, 02RH47Z, 02RH48Z, 02RH4JZ, 02RH4KZ, 02RJ07Z, 02RJ08Z, 02RJ0JZ, 02RJ0KZ, 02RJ47Z, 02RJ48Z, 02RJ4JZ, 02RJ4KZ, 02RF07Z, 02RF08Z, 02RF0KZ, 02RF47Z, 02RF48Z, 02RF4KZ, X2RF032, X2RF432, 02RF0JZ, 02RF4JZ, 02RG07Z, 02RG08Z, 02RG0KZ, 02RG37Z, 02RG38Z, 02RG3KZ, 02RG47Z, 02RG48Z, 02RG4KZ, 02RG0JZ, 02RG3JZ, 02RG4JZ, 02RH07Z, 02RH08Z, 02RH0KZ, 02RH47Z, 02RH48Z, 02RH4KZ, 02RH0JZ, 02RH4JZ, 02RJ07Z, 02RJ08Z, 02RJ0KZ, 02RJ47Z, 02RJ48Z, 02RJ4KZ, 02RJ0JZ, 02RJ4JZ	

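### The ICD-10 valvular-AF exclusion list in Appendix B Table 2 is wider than its ICD-9 counterpart and than the lesions named in Section 9.2, so eligibility depends on the coding era

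*Combined protocol and SAP*

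**What the plan says.** Section 9.2 (Subject Exclusion) sets the trigger for valvular AF at "Having at least one medical claim with any of the following diagnoses or procedures codes" in the pre-period. It names mitral stenosis alone, with insufficiency, with aortic stenosis and with aortic insufficiency. It does not name mitral insufficiency alone.

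Annex 1, Appendix B, Table 2 turns those names into codes:

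- Mitral stenosis: ICD-9 394.0x; ICD-10 "I05.0, I05.1, I05.2, I05.8, I05.9, I34.2".
- Mitral stenosis with insufficiency: ICD-9 394.2; ICD-10 "I34.0, I34.2, I34.8, I34.9".
- Mitral plus aortic stenosis: ICD-9 396.0; ICD-10 "I06.0, I35.0, Q23.0".
- Mitral stenosis plus aortic insufficiency: ICD-9 396.1; ICD-10 "I08.0, I06.1, I25.1, Q23.1, Q23.8, Q23.9".
- "Aortic valve valvuloplasty/diseases of aortic valve": ICD-9 395.x; ICD-10 I06.x.

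Section 9.11 states that "effort has been made to avoid exclusions that may differentially affect the treatment groups".

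**The concern.** Each combined-lesion row has one ICD-9 code but several ICD-10 codes, any one of which excludes. The row for combined mitral and aortic stenosis contains no I05 or I34 code, although those are the families the table uses for mitral disease. One claim from that row therefore meets a criterion named for a two-valve lesion without any mitral code.

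The rule applied to late entrants is then stricter than the rule applied to early ones, and the target population shifts at the coding switch. If the drug mix also changes over calendar time, the extra exclusions can fall unevenly on the treatment groups before matching. Section 9.11 says effort was made to avoid that.

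**Working it through.** The plan gives no figure for this point, so the check compares the two columns of Table 2 and then asks how much of the study the mismatch can reach.

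**1. Columns side by side.** For each ICD-10 code in the three combined-lesion rows, is it also listed in another row with its own ICD-9 code?

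| ICD-9 row | Also in another row | In no other row |
|---|---|---|
| 394.2 | I34.2 (394.0x) | I34.0, I34.8, I34.9 |
| 396.0 | I06.0 (395.x) | I35.0, Q23.0 |
| 396.1 | I06.1 (395.x) | I08.0, I25.1, Q23.1, Q23.8, Q23.9 |

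That is 3 ICD-9 codes against 4 + 3 + 6 = 13 ICD-10 codes. Three are matched elsewhere, leaving 10. I08.0 is itself a combined mitral-aortic code, leaving 9. I25.1 is a separate error: Appendix A Table 2 assigns I25.xxx to coronary artery disease. Eight codes remain.

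The mitral stenosis row adds three more. The ICD-9 column takes two members of the 394 family (394.0x, 394.2). The ICD-10 column takes five of I05 (I05.0, I05.1, I05.2, I05.8, I05.9). I05.1, I05.8 and I05.9 go beyond stenosis with or without insufficiency. Total: 8 + 3 = 11 codes. The ICD-9 column has no 394.1, 424.x or 746.x entry that could offset them.

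**2. Share of the entry window under ICD-10.** The documents give no switch date, so it is assumed. Share = days from switch to 30 June 2016 ÷ days in the index window.

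| Assumed switch | Rivaroxaban comparison | Apixaban comparison |
|---|---|---|
| 1 July 2015 | 20.0% | 28.5% |
| 1 October 2015 | 15.0% | 21.3% |
| 1 January 2016 | 9.9% | 14.1% |

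With a 1 October 2015 switch, the ICD-10 part of the 12-month look-back runs from 0 to 9 months, on average (0 + 9)/2 = 4.5 months with even entry after the switch. The wider list therefore acts on only part of most affected baselines.

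**3. Does the drug mix shift over time?** The Abstract (Study size) gives 16,604 dabigatran patients from July 2011 and 6,050 from 28 December 2012, both to June 2016. Assume the second count is nested in the first.

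- First 18 months: 16,604 − 6,050 = 10,554, which is 10,554/16,604 = 64%, or about 586 per month.
- Last 42 months: 6,050/42 = about 144 per month.
- All 20,930 apixaban patients fall in those 42 months: about 498 per month.

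With a 1 October 2015 switch and even entry within each segment, 9 × 144 = 1,296 dabigatran patients enter under ICD-10, or 7.8% of 16,604. Even entry of rivaroxaban patients would put 15% of them there. For 6 and 12 ICD-10 months the pairs are about 5.2% against 10%, and 10.4% against 20%. The rivaroxaban entry profile is not given, so these contrasts are conditional.

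**4. Power, for context.** Section 9.5 assumes 16,000 × 0.9 = 14,400 matched pairs, 3.1% per year and 0.82 years. For a ratio of 1.22, expected events are 14,400 × 0.031 × 0.82 × 2.22 = 813. Power = Φ(√(813/4) × ln 1.22 − 1.96) = 0.81, which agrees with the plan's 80%. An illustrative 5% loss of matched patients gives 0.79. The issue is comparability over time, not power.

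**The case against.** The best defence has four parts.

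- **Matching.** The same list applies to every drug on a given date and uses baseline claims only. The Abstract says the propensity models will include month and year of index date, so late entrants would mostly be compared with late entrants. This stands as a limit on confounding, although Section 9.7 only lists the variable for consideration. It does not keep the population constant: matching cannot bring back excluded patients. Valve disease is also not among the covariates named in Section 9.3.3, so early entrants with these lesions stay in and the lesion is not a listed matching variable.
- **Intent.** The 395.x row shows that stand-alone aortic valve disease is a deliberate exclusion, so the sponsor may have wanted a broad definition. That is possible, but the ICD-9 column and Section 9.2 would then have to say so.
- **Outside knowledge.** The plan does not print the meanings of I34.0, I35.0 or the Q23 codes. Reading them as single-valve or unspecified conditions relies on the standard code set. The row-to-row asymmetry is visible without it.
- **Overlap.** I25.1 sits in the same block and is the clearer error. One correction can cover both, but removing I25.1 alone leaves the other eleven codes.

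**Conclusion.** The point stands as a correction that should be made: eleven ICD-10 codes widen the valvular exclusion beyond both its ICD-9 counterpart and Section 9.2. It rests on the code lists as printed, on the single-claim trigger and, for what individual codes mean, on the standard classification.

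A reader might infer more than the documents support:

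- **That every aortic code is unmatched, or every combined lesion is split.** I06.0 and I06.1 are matched through 395.x, and I08.0 remains a combined code.
- **A patient count, from an assumed carriage rate and even entry.** The documents give no prevalence, the dabigatran counts contradict even entry, and it is unclear whether the feasibility counts already reflect these exclusions. The number affected cannot be computed.
- **That the arms are biased, or that Section 9.11 is contradicted.** The drug mix appears to shift over time, so unequal exclusion before matching is plausible. Bias in the matched comparison is not shown, and Section 9.11 claims only that effort was made.

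**What to change.** Make the two columns of Appendix B Table 2 equivalent.

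- **Preferred:** limit ICD-10 to the lesions named in Section 9.2. Remove I34.0, I34.8, I34.9, I35.0, Q23.0, Q23.1, Q23.8, Q23.9, I05.1, I05.8 and I05.9 as stand-alone exclusions. For the mitral-plus-aortic rows, keep I08.0 or require a mitral stenosis code together with an aortic code. Leave I06.x under the 395.x row.
- **If the wider definition is intended:** add the corresponding ICD-9 codes and name the lesions in Section 9.2.

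Correct I25.1 in the same edit, and report valvular exclusions by drug and coding period.

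The edit itself is small. Section 6 schedules programming-rule work from 19 October 2016 and analysis from 5 December 2016, and the protocol is dated 15 December 2016. Cohort selection may therefore have to be re-run. I08.0 cannot exactly reproduce 396.0 and 396.1, so some mismatch will remain and should be stated.

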9.3.3 Covariates

The following variables, but not limited to, will be used as covariates in the relevant analysis:

- **Gender:** Gender will be determined from eligibility file. Dichotomous variable (male=1, female=0).
- **Age:** Age in years will be determined on the index date. Continuous variable.
- **Geographic location:** Geographic locations of patient residence will be determined from eligibility file and will be grouped based on the US census classification (i.e., Northeast, Midwest, South, and West regions). South region will be the reference location.
- **Health plan type:** Health plan benefit designs such as health maintenance organization (HMO), preferred provider organization (PPO), fee-for-service (FFS), Medicare Advantage and Part D plan, etc. FFS is the reference plan type.
- **Baseline comorbid conditions:** The comorbid conditions will be captured by any inpatient claim, any two physician office visit (OV) or emergency room (ER) visits,

or a combination of both (OV+ER) with a diagnosis of the following conditions in any position during baseline (12 month pre-index period) (See [Appendix A, Table 2](#), for ICD-9-CM) and ICD-10 codes:

- Cancer
- Rheumatoid arthritis
- Coronary artery disease
- Acute myocardial infarction
- Cardiomyopathy
- Ischemic stroke
- Stroke (all types)
- TIA
- Congestive heart failure
- Left ventricular heart failure
- Hypertension
- Peripheral artery disease
- Liver disease
- Renal disease
- COPD/emphysema
- Diabetes
- Peptic ulcer (bleeding or non-bleeding)
- GERD
- Venous thromboembolism
- Hyperlipidemia
- HIV infection
- Bone marrow disease (thrombocytopenia, chronic anemia, myelofibrosis)
- Coagulopathy (hemophilia, Von Willebrand disease)
- Chronic kidney disease
- **Baseline (pre-index) medication use**
 - **Non-Oral Anticoagulants:** Number of prescription fills (normalized to a 30-day supply) will be captured during the pre-index period (See [Appendix A, Table 8](#))
 - Argatroban (can be used in procedures in lieu of heparin)
 - Unfractionated Heparin (Heparin)
 - Low Molecular Weight Heparins:
 - Enoxaparin
 - Tinzaparin
 - Dalteparin
 - Fondaparinux
 - **Other medication use:** Use of other medications will be determined if patients had ever filled a medication in the following drug classes during the pre-index period (See [Appendix A, Table 3, Table 8](#)).
 - Beta blockers
 - Calcium channel blockers
 - Diuretics

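### A coronary disease code, I25.1, is listed among the valvular-AF exclusion codes, while the same code family is defined elsewhere as a baseline covariate

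*Combined protocol and SAP*

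**What the plan says.** Section 9.2 sends the reader to Appendix B for the inclusion and exclusion codes, so the appendix is the operative list. The valvular criterion in Section 9.2 begins "Having at least one medical claim with any of the following diagnoses or procedures codes in order to exclude patients with" valvular AF, and it applies to the pre-index period. A single claim is therefore enough to exclude.

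Appendix B Table 2 lists, for combined mitral stenosis and aortic insufficiency (ICD-9 396.1), the ICD-10 codes "I08.0, I06.1, I25.1, Q23.1, Q23.8, Q23.9". The row above, for combined mitral and aortic stenosis (ICD-9 396.0), lists "I06.0, I35.0, Q23.0".

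Appendix A Table 2 defines coronary artery disease by ICD-10 "I20.x, I24.x, I25.xxx" and ICD-9 "411.xx, 412.xx, 413.xx, 414.xx, 429.2". Section 9.3.3 lists coronary artery disease as a baseline comorbidity, "captured by any inpatient claim, any two physician office visit (OV) or emergency room (ER) visits" or a combination of the two. Section 9.7 makes those comorbidities candidates for the propensity score. Section 9.2 does not name coronary artery disease as an exclusion.

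**The concern.** The same code family defines both a reason for exclusion and a characteristic to be described and balanced among the patients retained. The two tables cannot both be right about I25.1.

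At stake is who enters the cohort. If a programmer treats I25.1 as a prefix, patients with non-valvular AF and coronary disease are dropped on one ICD-10 claim, while the same patients coded in ICD-9 stay in. Eligibility would then depend on the coding system in use during the baseline year. That sits poorly with the aim in Section 9.11 of avoiding exclusions that could act differently between groups. If the code is instead matched exactly, it probably catches almost no one, and the entry contributes nothing to the valve screen.

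**Working it through.** No power or rate calculation applies. The check compares the code lists.

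**1. Count the ICD-10 entries in the valvular rows of Appendix B Table 2.**

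| ICD-9 row | ICD-10 entries |
|---|---|
| 394.0x | 6 |
| 394.2 | 4 |
| 396.0 | 3 |
| 396.1 | 6 |
| 397.x | 7 |
| 398.9x | 3 |
| V42.2 | 2 |
| V43.3 (prosthetic valve) | 1 |
| V43.3 (atrioventricular repair) | 1 |
| 395.x | 1 |

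The total is 6 + 4 + 3 + 6 + 7 + 3 + 2 + 1 + 1 + 1 = 34. I34.2, I09.89 and Z95.2 each appear twice, so 34 − 3 = 31 are distinct. By category: I05 5, I06 3, I07 1, I08 6, I09 3, I25 1, I34 4, I35 1, Q23 4, Z95 3, which again sums to 31.

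**2. Compare these with the ICD-10 ranges in Appendix A Table 2.** Only I25.1 falls inside one of them (coronary artery disease, I25.xxx).

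**3. Compare the ICD-9 columns.** The valvular rows use 394.0x, 394.2, 395.x, 396.0, 396.1, 397.x, 398.9x, V42.2 and V43.3. Coronary artery disease uses 411–414 and 429.2. They do not overlap, so the conflict exists only for claims coded in ICD-10.

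**4. Compare the two adjacent rows.** The 396.0 row has I06.0, I35.0 and Q23.0. The 396.1 row has I06.1, I25.1 and Q23.1 in parallel positions. The pattern suggests a one-digit slip for I35.1, and I35.1 appears in no row of the table. This is an inference; the documents do not establish which code was intended.

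**5. Work through the two possible matching rules.**

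- *Exact match.* Appendix B Table 2 marks families with x, as in "I80.xxx, I82.xxx" and "I07.x, I09.89, I08.1, I08.2, I08.3, I08.8, I08.9", and I25.1 carries none, so exact matching is the more natural reading. If claims carry coronary codes in a longer form, as the I25.xxx notation suggests, about zero patients are wrongly excluded. The loss of screening is also small. The condition named in the row includes mitral stenosis, which a separate row screens through I05.0 and I34.2, and the other five codes in this row still work.
- *Prefix match.* Any patient with one pre-index claim in the I25.1 family is removed. Recording coronary disease as a covariate needs more than that: an inpatient claim or two office or ER visits. Every ICD-10-coded patient whose coronary covariate rests on I25.1 codes would therefore already be excluded. The covariate would then be populated differently under ICD-9 and ICD-10.

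The documents give neither the prevalence of coronary disease nor the number of baselines coded in ICD-10, so no patient count can be put on the prefix case.

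**The case against.** The strongest objection is that this is one digit in a table read from a PDF by a program. If the original reads I35.1, nothing remains of the point. That stands, and it is why the original must be checked first. The myocarditis row of the same table contains I511.4, a malformed code, so a digit error there is plausible, whether typed or introduced in reading.

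Second, overlap between tables does not by itself prove an entry wrong. I09.81 is a valvular exclusion code and also a heart-failure code in Appendix A Table 6. ICD-9 423.2 is both a pericarditis exclusion and a liver-disease covariate code. This is fair as a caution. But I09.81 has a matching ICD-9 partner (398.91, within the valvular row's 398.9x), so the two coding systems agree there. I25.1 has no such partner.

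Third, the effect is near zero under exact matching. That is true if exact matching is used, but the plan never states the rule and its x notation is not consistent. Hematuria is 599.7x in Appendix A Table 7 and 599.7 in Table 9; 569.3 and 578.1 in Table 7 become 569.3x and 578.1x in Table 9. The prefix reading is less likely but cannot be ruled out.

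Fourth, the one-claim trigger applies to every valvular row and is not a fault of I25.1. Agreed; it matters here only because it sets how little would be needed to remove a coronary patient. Fifth, month and year of index date are candidate propensity-score variables, which would partly absorb a difference that follows calendar time. Also agreed.

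**Conclusion.** The point holds, at minor severity. As the text stands, the 396.1 row contains a code that the plan itself defines as coronary artery disease, in a rule that decides eligibility: one entry of 34, or of 31 distinct. Under exact matching the practical effect is about nil. Under prefix matching it would remove ICD-10-coded coronary patients in a number that cannot be derived from the documents. Bias between arms should be limited either way, because the rule is applied before treatment and is the same in both arms.

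The conclusion assumes that the original document shows the same digit. That I35.1 was intended is plausible but unconfirmed, and the conclusion does not depend on it.

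**What to change.** Check the 396.1 row of Appendix B Table 2 against the original document. If I25.1 is there, remove it so that Appendix A Table 2 and Appendix B Table 2 agree, and put another code in its place only if the sponsor confirms which valve code was meant. Report in the attrition table how many patients this row alone removes. Add one line stating that ICD codes written without x are matched exactly.

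The cost is one code edit, one sentence and one attrition count. No new data are needed.
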